7.2. Screening and Critical Baseline Assessments

Medical history, including cardiovascular disease and associated risk factors, (as detailed in the eCRF) will be assessed at screening.

The following demographic parameters will be captured: year of birth, sex, race and ethnicity.

Medical/medication/family history will be assessed as related to the inclusion/exclusion criteria listed in Section 5.

7.3. Safety

7.3.1. Adverse Events (AE) and Serious Adverse Events (SAEs)

The definitions of an AE or SAE can be found in Section 12.4.

The investigator and their designees are responsible for detecting, documenting and reporting events that meet the definition of an AE or SAE.

7.3.1.1. Time Period and Frequency for Collecting AE and SAE Information

- Any SAEs assessed as related to study participation (e.g., protocol-mandated procedures, invasive tests, or change in existing therapy) or related to a GSK product will be recorded from the time a subject consents to participate in the study up to and including any follow-up contact.
- AEs will be collected from the start of washout until the follow-up contact (see Section 7.3.1.3), at the timepoints specified in the Time and Events Table (Section 7.1).
- Medical occurrences that begin prior to the start of washout but after obtaining informed consent may be recorded on the Medical History/Current Medical Conditions section of the CRF.
- All SAEs will be recorded and reported to GSK within 24 hours, as indicated in Section 12.4. The investigator will submit any updated SAE data to the sponsor within 24 hours of it being available.
- Investigators are not obligated to actively seek AEs or SAEs in former study subjects. However, if the investigator learns of any SAE, including a death, at any time after a subject has been discharged from the study, and he/she considers the event reasonably related to the study treatment or study participation, the investigator must promptly notify GSK.

NOTE: The method of recording, evaluating and assessing causality of AEs and SAEs plus procedures for completing and transmitting SAE reports to GSK are provided in Section 12.4.

7.3.1.2. Method of Detecting AEs and SAEs

Care must be taken not to introduce bias when detecting AEs and/or SAEs. Open-ended and non-leading verbal questioning of the subject is the preferred method to inquire about AE occurrence. Appropriate questions include:

- “How are you feeling?”
- “Have you had any (other) medical problems since your last visit/contact?”
- “Have you taken any new medicines, other than those provided in this study, since your last visit/contact?”

7.3.1.3. Follow-up of AEs and SAEs

After the initial AE/SAE report, the investigator is required to proactively follow each subject at subsequent visits/contacts. All SAEs, and AEs of Special Interest (as defined in Section 7.3.1.4) will be followed until resolution, until the condition stabilizes, until the event is otherwise explained, or until the subject is lost to follow-up (as defined in Section 5.5). Further information on follow-up procedures is given in Section 12.4.5.

7.3.1.4. Adverse Events of Special Interest

The investigator or site staff will be responsible for detecting, documenting and reporting any AEs of special interest or any event that may potentially be one of the categories listed below (using preferred terms):

- Death, myocardial infarction (MI), stroke, heart failure, thromboembolic events, thrombosis of vascular access
- Thrombosis and/or tissue ischemia secondary to excessive erythropoiesis
- Cardiomyopathy
- Pulmonary artery hypertension (see also Section 7.3.1.5)
- Cancer-related mortality and tumor progression and recurrence
- Esophageal and gastric erosions
- Proliferative retinopathy, macular edema, choroidal neovascularization
- Exacerbation of rheumatoid arthritis
- Worsening of hypertension

The results of any investigation should be recorded in the relevant sections of the subject’s eCRF.

7.3.1.5. Cardiovascular and Death Events

GSK has identified CV and death events of special interest for all clinical studies. Investigators will be required to fill out the specific CV event page of the eCRF for the CV AEs and SAEs or any event that may potentially be one of the categories listed in Section 12.4.3.

7.3.1.6. Regulatory Reporting Requirements for SAEs

Prompt notification by the investigator to GSK of SAEs related to study treatment is essential so that legal obligations and ethical responsibilities towards the safety of subjects and the safety of a product under clinical investigation are met.

GSK has a legal responsibility to notify both the local regulatory authority and other regulatory agencies about the safety of a product under clinical investigation. GSK will comply with country specific regulatory requirements relating to safety reporting to the regulatory authority, Institutional Review Board (IRB)/Independent Ethics Committee (IEC) and investigators.

Investigator safety reports are prepared for suspected unexpected serious adverse reactions according to local regulatory requirements and GSK policy and are forwarded to investigators as necessary.

An investigator who receives an investigator safety report describing a SAE(s) or other specific safety information (e.g., summary or listing of SAEs) from GSK will file it with the IB and will notify the IRB/IEC, if appropriate according to local requirements.

7.3.1.7. Possible Suicidality Related Adverse Events

If during the study there is an occurrence of an AE or SAE which in the investigator's opinion, is possibly related to suicidality, the Possible Suicidality Related Adverse Events (PSRAE) eCRF form should be completed (in addition to the AE and SAE pages, as appropriate).

This event may include, but is not limited to, one that involves suicidal ideation, a preparatory act toward imminent suicidal behavior, a suicide attempt, or a completed suicide. The investigator will exercise his or her medical and scientific judgment in deciding whether an event is possibly related to suicidality.

7.3.2. Pregnancy

Details of all pregnancies in female subjects and the outcome for the neonate, if applicable, will be collected after the start of dosing and until 14 days post-last dose. If a pregnancy is reported, then the investigator should inform GSK within 2 weeks of learning of the pregnancy and should follow the procedures outlined in Section 12.4.8.

7.3.3. Physical Exams

A complete physical examination will include, at a minimum, assessment of the cardiovascular, respiratory, gastrointestinal and neurological systems.

- Investigators should pay special attention to clinical signs related to previous serious illnesses.
- For height and weight measurements, the subject is recommended to wear indoor, daytime clothing with no shoes.

7.3.4. Vital Signs and Weight

Vital signs will be measured with the subject in a semi-supine position after 5 minutes rest and will include temperature, systolic and diastolic blood pressure and heart rate, and will be measured both pre- and post-dialysis.

Weight will be measured both pre- and post-dialysis and recorded as specified in the Time and Events Table (Section 7.1).

7.3.5. Electrocardiogram (ECG)

ECG measurements will be taken at the time points specified in the Time and Events Table (Section 7.1). Full 12-lead ECGs will be recorded with the subject in a supine position. Heart rate (HR), PR interval, QRS duration, and QT (uncorrected) interval will be measured. QTcB will be calculated (machine-read or manually).

At the Screening visit two additional ECGs are required if the initial ECG indicates prolonged QTc (see Section 5.3) using the automated or manually calculated QTcB value. The average QTcB value of all three ECGs will be used to determine eligibility. Additional details are provided in the SRM.

ECG data will be read locally.

All ECGs will be performed before measurement of vital signs and collection of blood samples for laboratory testing.

7.3.6. Clinical Safety Laboratory Assessments

All protocol required laboratory assessments, as defined in Table 5 must be conducted in accordance with the Laboratory Manual, and Protocol Time and Events Schedule. Laboratory requisition forms must be completed and samples must be clearly labelled with the subject number, protocol number, site/center number, and visit date. Details for the preparation and shipment of samples will be provided by the laboratory and are detailed in the SRM. Reference ranges for all safety parameters will be provided to the site by the laboratory responsible for the assessments.

If additional non-protocol specified laboratory assessments are performed at the institution's local laboratory and result in a change in subject management or are considered clinically significant by the investigator (e.g., SAE or AE or dose modification) the results must be recorded in the eCRF.

Refer to the SRM for appropriate processing and handling of samples to avoid duplicate and/or additional blood draws.

All study-required laboratory assessments will be performed by a central laboratory, apart from HemoCue Hgb. The results of each HemoCue test must be entered into the eCRF.

NOTE: Local laboratory results are only required in the event that the central laboratory results are not available in time for either a treatment and/or response evaluation to be performed. If a local sample is required, it is important that the sample for central

analysis is obtained at the same time. Additionally if the local laboratory results are used to make either a treatment or response evaluation, the results must be entered into the eCRF.

Hematology, clinical chemistry, and additional parameters to be tested are listed in [Table 5](#).

Table 5 Protocol Required Safety Laboratory Assessments

Laboratory Assessments	Parameters		
Hematology	Platelet Count	RBC Indices:	WBC Count with Differential:
	RBC Count	MCV	Neutrophils
	Hemoglobin	MCH	Lymphocytes
	Hematocrit	MCHC	Monocytes
	WBC Count (absolute)	RDW	Eosinophils
	Reticulocyte Count	CHr	Basophils
Clinical Chemistry	Potassium	AST (SGOT)	Total and direct/indirect bilirubin
	Sodium	ALT (SGPT)	Total Protein
	Glucose	Calcium (Albumin adjusted)	Alkaline Phosphatase
	Albumin	Phosphate	
Other Screening Tests	Serum hCG pregnancy test	Serum ferritin	Folate
	Estradiol ¹	Serum iron	Vitamin B12
	FSH ¹	Serum transferrin	UIBC
		TSAT	

NOTE: Details of Liver Chemistry Stopping Criteria and Required Actions and Follow-Up Assessments after liver stopping or monitoring event are given in Section 12.2.

¹ As needed in women of non-child bearing potential only.

Abbreviations: ALT= Alanine transaminase; AST= Aspartate transaminase; CHr=Reticulocyte hemoglobin content; FSH=follicle stimulating hormone; MCH= Mean corpuscular hemoglobin; MCHC= Mean corpuscular hemoglobin concentration; MCV= Mean corpuscular volume; RBC= Red blood cell; RDW= Red blood cell distribution width; SGOT=Serum glutamic oxaloacetic transaminase; SGPT=Serum glutamic-pyruvic transaminase; TSAT = transferrin saturation; UIBC= unsaturated iron binding capacity; WBC= White blood cells;

All laboratory tests with values that are considered clinically significantly abnormal during participation in the study or within 14 (\pm 3) days after the last dose of study treatment should be repeated until the values return to normal or baseline. If such values do not return to normal within a period judged reasonable by the investigator, the etiology should be identified and the sponsor notified.

7.4. Pharmacokinetics

7.4.1. Blood Sample Collection

Blood samples for pharmacokinetic (PK) analysis of daprodustat and its metabolites (GSK2391220 [M2], GSK2531403 [M3], GSK2487818 [M4], GSK2506102 [M5], GSK2531398 [M6], and GSK2531401 [M13]) will be collected at the time points indicated in Section 7.1, Time and Events Table. The actual date and time of each blood

sample collection will be recorded. The timing of PK samples may be altered and/or PK samples may be obtained at additional time points to ensure thorough PK monitoring.

Details of PK blood sample collection (including volume to be collected), processing, storage and shipping procedures are provided in the SRM.

If the subject is unable to provide a sufficient blood quantity per time point or there is significant concern for this by the subject or investigator, these serial blood draws may be omitted.

7.4.2. Sample Analysis

Plasma analysis will be performed under the control of Bioanalysis, Immunogenicity, and Biomarkers - In Vitro/In Vivo Translation Platform/Scinovo, GlaxoSmithKline, the details of which will be included in the SRM. Concentrations of daprodustat and its metabolites (GSK2391220 [M2], GSK2531403 [M3], GSK2487818 [M4], GSK2506102 [M5], GSK2531398 [M6], and GSK2531401 [M13]) will be determined in plasma samples using the currently approved bioanalytical methodology. Raw data will be archived at the bioanalytical site (detailed in the SRM).

7.5. Biomarker(s)/Pharmacodynamic Markers

7.5.1. Ambulatory Blood Pressure Monitoring (ABPM)

Blood pressure and pulse will be measured during Acute Challenge 1 and 2 through the use of an ambulatory blood pressure monitoring device. Subjects will wear the ABPM device for two sessions during the study (i.e., Acute Challenge 1 and 2), occurring at Day 1 (randomization) and at Day 57. The ABPM device will be placed prior to Acute Challenge dosing, and will remain on the subject's arm until 24 hrs post-dosing.

ABPM measurements of systolic and diastolic blood pressure and heart rate will be automatically recorded every 15 minutes for the first 6 hrs post-dosing, and then every 20 minutes thereafter until 24 hrs post-dosing. The ABPM device will automatically calculate MAP.

The device planned for use in this study is the Mortara Ambulo 2400; a specification sheet for this device can be found in Section [12.6](#).

After both Acute Challenge 1 and 2, the 24-hr ABPM results will be checked for data quality as defined in the Project Requirement Specification (PRS). If the ABPM fails the QC criteria following Acute Challenge 2, one additional Acute Challenge may be made in a subsequent, mid-week dialysis visit 1 week later if the subject agrees. At that visit, the subject will receive the same study treatment for the repeat Acute Challenge 2 as was administered on Day 57 as a single additional dose. No additional clinical chemistry, hematology, pharmacokinetic or biomarker sampling will be done, however all other procedures will be performed as detailed in [Table 4](#).

7.5.1.1. ABPM Delay Due to High Hgb

Day 1: If the HemoCue Hgb is confirmed to be ≥ 11.5 g/dL, then avoid dosing and continue washout for one additional week. No other assessments should be performed for that subject during the visit. When the subject returns 7 days later, re-draw the Hgb for HemoCue and assess. If confirmed to be < 11.5 g/dL then progress with the remainder of assessments and perform Acute Challenge 1. If the Hgb remains high, the subject must be withdrawn.

Day 57: If the HemoCue Hgb is confirmed to be ≥ 11.5 g/dL, then hold the dose(s) of IP for 1 week. No other assessments should be performed for that subject during the visit. When the subject returns 7 days later, re-draw the Hgb for HemoCue and assess. If confirmed to be < 11.5 g/dL then progress with the remainder of assessments and perform Acute Challenge 2. If the Hgb remains high, the subject must be withdrawn.

7.5.2. Blood Pressure Regulation Biomarkers

Blood samples will be collected during this study to investigate the mechanism of the effect of daprodustat on blood pressure. Biomarkers selected will explore the renin-angiotensin-aldosterone axis, the nitric oxide and endothelin axes, sodium retention and HIF signalling.

Biomarkers may include erythropoietin, nitric oxide (NO), asymmetric dimethylarginine (ADMA), renin, angiotensin-II (1-8) and metabolites (1-7 and 1-5), endothelin-1 (ET-1), and noradrenalin. Samples will be collected as specified in the Time and Events Table (Section 7.1). The timing of the collections may be adjusted on the basis of emerging pharmacokinetic or pharmacodynamic (PD) data from this study or other new information in order to ensure optimal evaluation of the PD endpoints.

If the subject is unable to provide a sufficient blood quantity per time point or there is significant concern for this by the subject or investigator, these serial blood draws may be omitted.

7.6. Genetics

Genetics are not evaluated in this study.

8. DATA MANAGEMENT

- For this study, subject data will be entered into GSK defined electronic case report forms (eCRFs), transmitted electronically to GSK or designee and combined with data provided from other sources in a validated data system.
- Management of clinical data will be performed in accordance with applicable GSK standards and data cleaning procedures to ensure the integrity of the data, e.g., removing errors and inconsistencies in the data.
- Adverse events and concomitant medications terms will be coded using MedDRA (Medical Dictionary for Regulatory Activities) and an internal validated medication dictionary, GSKDrug.

- CRFs (including queries and audit trails) will be retained by GSK, and copies will be sent to the investigator to maintain as the investigator copy. Subject initials will not be collected or transmitted to GSK according to GSK policy.

9. STATISTICAL CONSIDERATIONS AND DATA ANALYSES

The primary endpoint for this study is average systolic blood pressure (SBP) over 6 hours of measurements taken at 15-minute intervals after the administration of study treatment for the Acute Challenge 2. The primary comparison of interest is daprodustat versus epoetin alfa for this challenge.

The comparison of daprodustat versus epoetin alfa on 6 hr average SBP during Acute Challenge 1 is a secondary endpoint.

9.1. Hypotheses

Null Hypothesis: The difference between 24 mg daprodustat versus 100 IU/kg epoetin alfa on 6 hr average SBP under a background of treatment (i.e., during Acute Challenge 2) is zero.

Alternative Hypothesis: The difference between 24 mg daprodustat versus 100 IU/kg epoetin alfa on 6 hr average SBP under a background of treatment (i.e. during Acute Challenge 2) is not zero.

9.2. Sample Size Considerations

9.2.1. Sample Size Assumptions

It is expected that 31 subjects will be randomized into each treatment arm. Assuming a 20% withdrawal rate during the Hgb Maintenance Period, there will be 25 subjects per treatment arm that will undertake Acute Challenge 2. The study will continue to recruit subjects until it is projected that 25 subjects per treatment arm complete and pass QC for Acute Challenge 2.

Assuming a 5% significance level and a true standard deviation (SD) of 16 mmHg for average SBP over 6 hours, a sample size of 25 subjects per treatment group will provide greater than 90% power to detect a -15 mmHg difference between treatment groups. Under these assumptions, statistical significance will be obtained if there is more than a 9.1 mmHg mean difference observed in favor of daprodustat.

Table 6 Power and Half-width of 95% CI for pair-wise comparisons, assuming a 16 mmHg SD for average SBP over 6 hours

Challenge	Expected Number of Subjects per Treatment Group	Power to detect 15 mm Hg difference	Half-Width of 95% CI ²
Acute Challenge 1	31	95%	8.1 mmHg
Acute Challenge 2 ¹	25	90%	9.1 mmHg

¹ Primary Comparison² Minimal detectable effect

9.2.2. Sample Size Sensitivity

Changes to power and the half-width of the 95% confidence interval for Acute Challenge 2 due to varying assumptions on the SD for average SBP over 6 hr are explored in [Table 7](#) below.

Table 7 Half-width of 95% CI for pair-wise comparisons, assuming 25 subjects per treatment group

Common SD for average SBP over 6 hours	Power to detect 15 mm Hg difference	Half-Width of 95% CI
14	96%	8.0 mmHg
16 [†]	90%	9.1 mmHg
18	82%	10.2 mmHg
20	74%	11.4 mmHg

[†] Primary Comparison

9.2.3. Sample Size Re-estimation or Adjustment

Subjects that withdraw prior to the Acute Challenge 2 assessment will be replaced so that 25 subjects per treatment arm complete Acute Challenge 2.

9.3. Data Analysis Considerations

9.3.1. Analysis Populations

The primary population of interest is the intent to treat (ITT) population defined as all randomized subjects that received at least one dose of study treatment.

In addition, a per-protocol population may be investigated. Details will be provided in the Reporting and Analysis Plan (RAP) for the study.

9.3.2. Interim Analysis

No interim analyses are currently planned for this study.

9.4. Key Elements of Analysis Plan

9.4.1. Primary Analyses

The primary analysis of average SBP over 6 hr post-dose during Acute Challenge 2 will be an analysis of covariance (ANCOVA) with terms for treatment, prior ESA dose (low/high), and post-HD/pre-Acute Challenge 1 SBP, difference between post-HD/pre-Acute Challenge 2 SBP and post-HD/pre-Acute Challenge 1 SBP, and treatment by (difference in post-HD SBP between Acute Challenge 1 and 2) interaction. Note that the pre-challenge SBP may change over time between Acute Challenge 1 and Acute Challenge 2 as a result of the maintenance therapy, and thus the pre-challenge SBP at Acute Challenge 2 is not a true pre-treatment covariate. As a result, the interpretation of the effect of the Acute Challenge 2 may be confounded by the impact of treatment phase on the covariate. Therefore, if the interaction term in this model is significant at the 0.10 level, then the primary model will be ANCOVA with terms for treatment, prior ESA dose (low/high), and post-HD/pre-Acute Challenge 1 SBP. The primary model will provide a point estimate and two-sided 95% CI for the treatment effect and a p-value for the superiority assessment. Superiority will be established if the p-value is <0.05.

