2.1. Study Rationale

Current labelling for all ESAs includes a contraindication in patients with uncontrolled hypertension, and increases in blood pressure (BP) and/or antihypertensive medication use has been observed in several clinical trials with ESAs. While the mechanism for this hypertensive effect is not known, hypertension has been consistently observed in approximately 25 to 30% of CKD patients initiating ESA therapy, and varies between an average of approximately 5 to 8 mmHg in systolic blood pressure (SBP), and 4 to 6 mmHg in diastolic blood pressure (DBP) reviewed in [Krapf, 2009]. Additionally, increases in BP are a well-recognized risk factor for CV events, in particular heart failure, ischemic stroke and myocardial infarction [Rodriguez, 2014]. Finally, treatment with ESAs has been associated with increased risk of major CV events including myocardial infarction, stroke and death.

Daprodustat has been shown to effectively raise and manage Hgb levels in subjects with CKD with lower levels of EPO than the ESAs. As the hypertensive effects of ESAs appear dose-related [Abraham, 1991], there is the potential that daprodustat can treat anemia in CKD patients without the hypertensive effects observed with the ESAs. This study will use two 24-hr Acute Challenges to compare the effect of daprodustat to rhEPO on BP as measured by ambulatory blood pressure monitoring (ABPM) following both a 2-week ESA washout period (Acute Challenge 1) and an 8-week Hgb-maintenance period (Acute Challenge 2).

Therefore, the purpose of this study is to compare the effects on blood pressure of daprodustat to epoetin alfa in hemodialysis-dependent (HD) subjects with anemia associated with CKD. The study will also assess various biomarkers associated with

blood pressure physiology that may provide insight into the mechanism(s) of the hypertensive effects associated with ESAs.

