7.1. Time and Events Table
Table 3 Study Procedures and Assessments

Procedure ¹	Screening	Washout	Treatment Period ²					Follow-up ²	
			Day 1	Day 15	Day 29	Day 43	Day 57	Early WD	Week 10
Informed Consent	X								
Entry Criteria	X								
Physical, Medical History, Demography	X								
HemoCue Hgb	X	X	X ⁴	X	X	X	X ⁴	X	X
Enrolment		X							
IVWRS			X	X	X	X			
Randomization			X						
Acute Challenge			X ⁴				X ⁴		
ABPM Assessment			X ⁴				X ⁴		
Dose Adjustment				X	X	X			
Females Only: Serum Pregnancy Test	X		X		X		X		X
Females Only: Estradiol & FSH (if required) ³	X								
ECG	X		X ⁴				X ⁴		X
Vital signs & weight (Pre- & Post-dialysis)	X	X	X ⁴		X		X ⁴		X
Clinical Chemistry	X		X		X		X		X
Hematology	X		X		X		X		X
Folate and Vitamin B12	X								
Ferritin, transferrin, total iron, TSAT, UIBC	X								
Pharmacokinetic/Biomarker Assessments			X ⁴				X ⁴		
Hgb Maintenance Period ⁵			←-----→						
Adverse Events Assessment	X ⁶	X	X ⁴	X	X	X	X ⁴		X
Review Concomitant Medications	X	X	X ⁴	X	X	X	X ⁴		X

1 All assessments should be done predialysis/predose except as noted.

2 Allowable time window ± 2 days EXCEPT Follow-up Visit which is ± 3 days.

3 As detailed in Inclusion Criteria.

4 Detailed timings for assessments on Acute Challenge Days are given in [Table 4](#).

5 From the end of Acute Challenge 1 to the beginning of Acute Challenge 2.

6 Only SAEs assessed as related to study participation are collected at this visit. See Section [12.4](#) for additional details.

Table 4 Study Procedures and Assessments on Acute Challenge Days (Treatment Period Day 1 and Day 57)

Procedure	Pre-Dialysis	Post-Dialysis	Predose	Time (in hours relative to dosing)										
				0	0.5	1	2	3	4	6	8	12	16	24
HemoCue Hgb ¹			X											X
IVWRS			X											
ABPM Assessment ^{1,3}			←=====→											
Administer Study Treatment ¹				X										
Serum Pregnancy Test ¹			X											
ECG ¹			X											X
Vital Signs and Weight ¹	X	X						X				X		X
Clinical Chemistry			X											
Hematology			X											
Pharmacokinetics ⁴			X		X	X	X	X	X	X	X	X	X	X
Erythropoietin			X		X	X	X	X	X	X	X	X	X	X
Endothelin-1			X		X	X		X	X	X				X
Nitric Oxide			X		X	X		X	X	X				X
Asymmetric dimethylarginine			X		X	X		X	X	X				X
Renin			X		X	X		X	X	X				X
Angiotensin-II			X		X	X		X	X	X				X
Noradrenalin			X		X	X		X	X	X				X
Adverse Events Assessment ¹			X		X	X	X	X	X	X	X	X	X	X
Review Concomitant Medications ¹			X											X
Initiate Hgb maintenance dosing ²														X

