9.4.2. Secondary Analyses

Average SBP over 6 hr post-dose in Acute Challenge 1 will be analyzed using ANCOVA with terms for treatment, prior ESA dose (low/high), and post-HD/pre-Acute Challenge 1 SBP. Similar analyses will be performed for DBP, MAP, and HR.

ANCOVA using the primary model will be used for the analysis of average DBP, MAP, and HR over 6 hr post-dose in Acute Challenge 2 replacing the baseline SBP term with the analogous baseline measurement for DBP, MAP, and HR respectively.

AUECs of SBP, DBP, MAP, and HR post Acute Challenge 2 and 1 will be analyzed using ANCOVA with terms for treatment and prior ESA dose (low/high) with 95% CIs and p-values provided for the treatment effect.

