DIMENSIONS	4.7 x 2.7 x 1.2" (119 x 68 x 32 mm)
WEIGHT	9.0 oz (253 g) (with batteries)
MEASUREMENT PRINCIPLE	Patented oscillometric technique with linear deflation.
MEASUREMENT RANGES	Systolic: 60 to 280 mmHg Diastolic: 30 to 160 mmHg Pulse Rate: 30 to 180 bpm
MEASUREMENT ACCURACY	Blood Pressure: ±3 mmHg mean difference ±8 mmHg standard deviation Pulse Rate: ±3 bpm According to ANSI/AAMI SP-10:2002 & BHS (Grade A/A) and ISO 81060-2:2009
MEASUREMENT INTERVALS	Four adjustable intervals during 24-hour periods, each configurable to 0, 5, 10, 15, 20, 25, 30, 45, 60, 75, 90, 105, or 120-minute measurements. Optional randomization factor up to 75% within intervals. Supports measurement over extended periods of time, typically 24 hours, and up to 7 days. Optional configuration support for Phase I clinical trials involving PK/PD dosing using discrete measurement time points based on protocol requirements. Measurements taken based on a sequence of time points until completed.
AVAILABLE CUFFS	Regular, large and small adult cuffs included. EasyWear™ cuff optional.
ACTIGRAPHY OPTION	Recording of 3-axis of motion via accelerometer for display and categorization of awake/asleep cycles via application software.
MEMORY	Solid-state Flash technology. Sufficient for 2,700 blood pressure measurements and 7 days of continuous actigraphy.
PC INTERFACE	USB
BATTERY POWER REQUIREMENTS	2 x 1.2V NiMH rechargeable batteries; 2.4V DC; Maximum current: 610mA. Sufficient for approximately 300 measurements using regular adult cuff.
SOFTWARE	Hypertension Diagnostics Suite requires PC running Microsoft Windows XP SP2, Windows Vista, or Windows 7 with a minimum graphics resolution of 1024 x 768.
MAXIMUM NOISE LEVEL	46 dBA during inflation; not measurable above ambient level during deflation

*Specifications subject to change without notice.

Ambulo™ is a trademark of Mortara Instrument, Inc.

Microsoft® and Windows® are registered trademarks of Microsoft Corporation in the United States and/or other countries.

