Post HD Pre Acute Challenge Variable					

 
The Post HD Pre Acute Challenge Variable data point will come from the SBP/DBP/HR/MAP reading recorded from the ABPM data. The zero time, first recorded measurement from the ABPM device, will be used as the post HD pre acute challenge variable 
 
If the data is missing from the ABPM data, the eCRF vital signs data will be used 
 
Post-dialysis measurement will be used
 
 
 
If MAP variable is needed from eCRF, MAP will be calculated the following way: 
 
MAP = (SBP + 2(DBP)) / 3
 
 
 
 
 
					
Difference between post-HD/pre-Acute Challenge 2 and post-HD/pre-Acute Challenge 1					
Difference between post-HD/pre-Acute Challenge 2 and post-HD/pre-Acute Challenge 1					

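### The Acute Challenge 1 model and the fallback primary model adjust for one pre-dose blood-pressure reading, although post-dialysis values from three pre-dose visits are collected and could add some precision

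*Protocol*

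**What the plan says.** Protocol 9.4.1 plans the primary analysis in two steps. The first-step ANCOVA has treatment, prior ESA dose, the pre-Acute Challenge 1 SBP, the change in pre-challenge SBP between the two challenges, and treatment by that change. If the interaction is significant at 0.10, the "primary model will be ANCOVA with terms for treatment, prior ESA dose (low/high), and post-HD/pre-Acute Challenge 1 SBP". Under Protocol 9.4.2, the 6-hour average SBP in Acute Challenge 1 "will be analyzed using ANCOVA with terms for treatment, prior ESA dose (low/high), and post-HD/pre-Acute Challenge 1 SBP". SAP 11.1.5.2 and 11.2.5.1 repeat these models.

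SAP 14.6.6 defines the covariate: "The zero time, first recorded measurement from the ABPM device, will be used as the post HD pre acute challenge variable". If that reading is unusable, the post-dialysis vital-sign value replaces it. If the Day 1 vital sign is also missing, the Week -2 or Screening value may be used.

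Protocol 7.1, Table 3, has a row "Vital signs & weight (Pre- & Post-dialysis" marked at Screening, Washout and Day 1. Protocol 7.3.4 confirms that vital signs include SBP, DBP and heart rate, measured before and after dialysis. SAP 5.4.1 allows further covariates to be considered but names none of this kind.

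**The concern.** One reading is a noisy measure of a subject's usual post-dialysis pressure. It carries the error of a single measurement and the variation of that particular day. Readings from other pre-dose visits carry information about the stable between-subject level, which is what predicts SBP eight weeks later. Leaving them out keeps explainable variance in the error term and makes the confidence interval wider than the collected data require.

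The point applies mainly to two models in which the single reading is the only blood-pressure covariate: the Acute Challenge 1 ANCOVA and the fallback primary ANCOVA. The first-step primary model also contains the pre-Acute Challenge 2 reading, so it has less to gain. However, Protocol 9.4.1 itself warns that this second reading is not a true pre-treatment covariate. The Screening, Washout and pre-dose Day 1 values do not have that problem.

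**Working it through.** **The plan's own figures.** Protocol 9.2.1 starts from "Assuming a 5% significance level and a true standard deviation (SD) of 16 mmHg for average SBP over 6 hours" and states that "a sample size of 25 subjects per treatment group will provide greater than 90% power to detect a -15 mmHg difference between treatment groups". A two-sided two-sample t-test (48 df, no covariates) gives power 90.1%. The half-width is 2.011 × 16 × sqrt(2/25) = 9.10 mmHg. Both match Table 6. The calculation takes no credit for any covariate, so nothing below undermines it.

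**Model for the gain (assumed).** The total variance of the 6-hour average is 16² = 256. The subject share is 50-70%, the visit-day share is 20-30%, and the rest is within-day. Single-reading error SD is 8-10 mmHg. The subject-level correlation between cuff and ABPM is k = 0.7-1.0. None of these splits is in the documents.

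**One case in full:** subject share 60%, visit share 20%, error SD 8, k = 0.8.

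- Subject variance is 0.6 × 256 = 153.6; visit variance is 0.2 × 256 = 51.2; error variance is 64.
- Day 1 ABPM reading x: variance 153.6 + 51.2 + 64 = 268.8.
- Mean c of three cuff values: variance 153.6 + (51.2 + 64)/3 = 192.
- cov(x, c) = 0.8 × 153.6 + 51.2/3 = 139.95, so r(x, c) = 139.95/sqrt(268.8 × 192) = 0.616.

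*Fallback primary model (25 per arm).*
- cov(x, Y) = 153.6, so R² with x alone = 153.6²/(268.8 × 256) = 0.343 and r(x, Y) = 0.586.
- cov(c, Y) = 0.8 × 153.6 = 122.88, so r(c, Y) = 122.88/sqrt(192 × 256) = 0.554.
- R² with both = (0.343 + 0.307 - 2 × 0.586 × 0.554 × 0.616)/(1 - 0.616²) = 0.403.
- CI ratio = sqrt((1 - 0.403)/(1 - 0.343)) = 0.953.
- Cost of the extra coefficient: residual df go from 46 to 45, a factor of about sqrt(45/44) = 1.011, and 1.012 with the change in t quantile.
- Net: 0.953 × 1.012 = 0.964, so 3.6% narrower (half-width about 7.38 to 7.12 mmHg).

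*Acute Challenge 1 (31 per arm).* The outcome now shares the Day 1 visit component.
- R² with x alone = 204.8²/(268.8 × 256) = 0.610.
- With c added, cov(c, Y) = 139.95 and R² = 0.646.
- The ratio is sqrt(0.354/0.390) = 0.952. With df from 58 to 57 (factor 1.009) the net is 0.961, so 3.9% narrower.

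*First-step primary model (main effects; df 44 to 43).* The pre-Acute Challenge 2 reading already brings R² to 0.638. Adding c gives 0.647. The ratio is 0.989 × 1.0125 = 1.001, so there is no gain in this case.

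**Range over 12 combinations** (subject share 50, 60, 70%; visit share 20, 30%; error SD 8, 10), percent narrowing net of the lost df:

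| k | Fallback primary | First-step primary | Acute Challenge 1 |
|---|---|---|---|
| 1.0 | 8 to 15 | 1 to 6 | 7 to 21 |
| 0.9 | 5 to 9 | 0 to 3 | 4 to 14 |
| 0.8 | 3 to 6 | 0 to 2 | 3 to 10 |
| 0.7 | 1 to 3 | -1 to 1 | 2 to 7 |

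**Add, do not replace.** Suppose a plain three-visit mean replaced the same-day reading in the Acute Challenge 1 model. Over a wider set of assumptions (subject share 40-70%, visit share 40-10%, error variance 60-200), the half-width goes from 5.02 to 5.88 mmHg (17% wider) at one end and from 6.28 to 5.33 mmHg (15% narrower) at the other. The same-day reading holds information that the other visits do not.

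**The case against.** The strongest reply is that nothing here is wrong. The latest same-day pre-dose value is a conventional, pre-specified baseline, and further covariates are permitted. The earlier readings are also imperfect repeats:

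- They are semi-supine cuff values, whereas the covariate comes from the ambulatory device.
- Screening and Washout both precede ESA withdrawal.
- The antihypertensive dose need be stable for only one week before Washout.
- Post-dialysis SBP above 160 mmHg at Screening is excluded, which truncates that value.
- Subjects enrolled before Amendment 3 had a different visit schedule.
- Where a cuff value has replaced the ABPM reading, the proposed mean overlaps with the existing covariate.

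All of this stands. It shrinks the gain, which is why k is taken down to 0.7 and the lower limits are small. It introduces no bias, because every value precedes the first dose.

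A reader might infer three stronger things that the documents do not support:

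- **That the trial is underpowered because of this.** Unadjusted power at 5 and 8 mmHg is 19% and 41%. However, the 5 to 8 mmHg in Protocol 2.1 is a rise in patients starting ESA therapy, not a 6-hour difference between two drugs after a challenge dose. The design targets 15 mmHg.
- **That the device sheet proves the reading is noisy.** Its "8 mmHg standard deviation" is an accuracy figure under validation standards, not within-subject repeatability. Here 8 mmHg only anchors an assumption.
- **That the primary analysis loses 9-16% of precision.** That range needs the fallback model, cuff and ABPM sharing an identical subject component, and no charge for the extra coefficient.

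**Conclusion.** The point holds as a modest efficiency improvement. The Acute Challenge 1 and fallback primary models use one pre-dose reading as their only blood-pressure covariate, and collected pre-dose values are otherwise left unused. Under the stated assumptions, adding them narrows the CI by about 2-21% for Acute Challenge 1 and 1-15% for the fallback primary model. The upper ends require cuff and ABPM to rank subjects almost identically. For the first-step primary model the effect is about -1 to 6%, so the addition there is optional and serves mainly consistency.

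The treatment estimate is unbiased either way, and Tables 6 and 7 are correct as stated. The size rests on variance shares and a cuff-ABPM correlation that the documents do not give, so no single figure should be quoted.

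**What to change.** In Protocol 9.4.1 and 9.4.2 and SAP 5.4.1, 11.1.5.2 and 11.2.5.1, keep every existing term, including the same-day ABPM reading. Pre-specify one added covariate: the mean of the available post-dialysis vital-sign SBP values at Screening, Washout and Day 1 before the first dose.

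- Use analogous means for DBP and HR, and for MAP calculated with the formula already in SAP 14.6.6.
- For subjects enrolled before Amendment 3, use the screening and washout averages that SAP 14.6.1 already defines.
- Apply it to the Acute Challenge 1 and fallback primary models. Including it in the first-step model is optional.
- Enter it as a separate covariate and do not pool it with the ABPM reading, because the two differ in method, posture and timing relative to ESA washout.

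The cost is one derived variable, SAP wording and one degree of freedom per model (46 to 45 in the fallback primary model, 58 to 57 for Acute Challenge 1, 44 to 43 in the first-step model). No new visits or measurements are needed. Because the study is open-label, the choice should be fixed in writing before database release.
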